#### **1.2.5.1 Preliminary Human Studies of Visualase Therapy in the Prostate**

[figure not shown]
Four patients underwent MRI guided laser ablation of the prostate using the Visualase system under a treat and resect protocol at the University of Toronto. No patients experienced complications from the ablation or post ablation prostatectomy. A personal communication with the lead investigator: to ask the question regarding difficulty of post ablation prostatectomy, he reports that the ablation did not increase the difficulty or complication associated with performing a post focal ablation prostatectomy. Comparing the MRI predicted ablation zone with whole mount histopathology showed a direct correlation.

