## **7.4 DATA AND SAFETY MONITORING PLAN**

### **7.4.1 Principal Investigator/Research Team**

The clinical research team will meet on a regular basis when patients are being actively treated on the trial to discuss each patient in detail.

All data will be collected in a timely manner and reviewed by the principal investigator or a lead associate investigator in a timely manner. Adverse events will be reported as required above. Any safety concerns, new information that might affect either the ethical and or scientific conduct of the trial, or protocol deviations will be immediately reported to the IRB using iRIS) and to the manufacturer.

In addition, the PI and associate investigators will monitor adverse events on an ongoing basis and modify the protocol and/or consent accordingly. After the first 5 patients are treated, and again after the first 10 are treated, interim assessments will be performed by the PI and associate investigators. This study will be stopped, and the IRB will be notified if adverse events develop which endanger patient safety, although the likelihood of this is so low that it is hard to create or imagine possible examples of such events.

The principal investigator will review adverse event and response data on each patient to ensure safety and data accuracy. The principal investigator will personally conduct or supervise the investigation and provide appropriate delegation of responsibilities to other members of the research staff. If there is mortality the study will be paused and a determination of cause will be pursued. If the cause was due to the laser therapy the pilot study will be concluded. Also, regarding other complications rates if the 30-day complication rate of serious events exceeds 2 patients a further analysis of the technique will be performed, as well as pausing and possible concluding the study if changes cannot be made for improvement.

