## **8 STATISTICAL SECTION**

The primary goal of this study is to assess the toxicity, performance and feasibility of the Visualase thermal therapy procedure for focal prostate cancer treatment and then to monitor any complications for the 3 years following treatment. The outcome measures of importance during the thermal treatment are pain, frequency of thermal damage outside of intended treatment areas as measured by post contrast MRI, frequency of not completing the entire procedure, or the frequency of other adverse events and complications. These outcome measures are further defined as follows:

- \* Observing thermal damage on post contrast MRI which extends into areas of the Rectum or Urethra will be considered side effects for stopping purposes.
- \* Frequency of not completing the procedure. Not completing the procedure for reasons other than those given above will be considered a side effect for stopping purposes.
- \* Other adverse events or complications that occur that are classified as Grade 3 or 4 by the National Cancer Institute's Common Toxicity Criteria 4, will be considered a side effect for stopping purposes.

Sample size

The purpose of the study is to assess the safety, performance and feasibility of the Visualase thermal therapy procedure for focal prostate cancer treatment. The sample size is targeted at 15 evaluable patients which is adequate to assess the toxicity rate and can be reasonably recruited in a 6-month period of time. With the accrual of 15 patients, the width of the 80% expected confidence interval of 0.1 and 0.2 toxicity rate is 0.19 and 0.26, respectively.

Stopping rule

For the purpose of protecting patient safety, we implement the following stopping rule for safety monitoring. If one patient experiences a grade 5 event, thought to be possibly or probably due to the laser therapy, the study will be stopped. For grade 3 or 4 event, the study will be stopped according to the following stopping rule.

Number of patients	No. of grade 3 or 4 serious adverse events
3-5	3
6-10	4
11-15	5

The operating characteristic of the stopping rule was assessed by simulations. Based on 10,000 simulations, the probability of stopping early for an excess of serious adverse event over the course of trial is 0.023 when the serious adverse event rate is 0.1 and 0.81 when the serious adverse event rate is 0.40. This is deemed reasonable for protecting patient safety.

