Frequency of the outcome measures, response and toxicity will be reported. Paired Student t test will be used to compare the difference between continuous variables (PSA, MRI imaging parameters) measured at baseline and at each follow-up visit. Prior to performing the paired t-test, the distribution of the underlying data will be assessed, and adequate transformation will be undertaken to ensure that the distribution of the transformed data is approximately normal. Descriptive statistics such as frequencies and percentages of categorical variables will be reported. In addition, McNemar's test, though may not have adequate power for this pilot study, will be explored to evaluate the difference in proportion between baseline and at each follow-up.

Longitudinal profiles of parameters recorded in the questionnaires over the course of follow-up for each patient will be plotted and the associated summary statistics such as mean, standard deviation, and mean change between successive follow-up visits will be reported. In addition, linear and non-linear mixed effects models will be explored to model the longitudinal profiles of the parameters of interest. In these models, random intercept will be used to incorporate the within-patient correlation of the repeated observations. If deemed appropriate, random slope will be added to the model to allow for the slope of profile to vary between patients.

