## **9.7 RISKS/BENEFITS ANALYSIS – MONITORING OF TRIAL**

Thus, we believe that this trial may eventually lead to improvements in the safety and delivery of ablation procedures. Although no guarantee of any benefit whatsoever will be made to the patient, experience from pre-clinical trials makes us confident that there is no increased risk to the patient from using the tracked devices that differ very little from conventional needles.

Focal thermal therapy for prostate cancer offers a treatment option intermediate between active surveillance and radical therapy for small volume, low grade prostate cancer. It prevents the side effects of radical therapy and may help decrease the chances of disease progression in active surveillance.

Potential risks associated with use of the Visualase laser thermal therapy system include bleeding, infection, pain, urinary tract symptoms, and damage to the rectal wall, bladder problems, and erectile dysfunction. Visualase applicator placement will be performed under sterile conditions with appropriate anesthesia (local, spinal, or general). If a course of prophylactic antibiotics or analgesics is administered according to standard clinical practice for this type of procedure, this information should be documented as a concomitant medication.

Potential risks associated with the thermal ablation treatment include pain, thermal injury to the adjacent organs, erectile dysfunction, the inability to urinate, and blood in the urine. MR-thermometry and feedback control using the Visualase system minimize the risk of overheating critical structures or areas outside of the intended target tissue.

No serious side effects or complications have been observed in any patients treated to-date with thermal ablation using Visualase.

Minimal risks are inherent within this protocol and include the physical risks of phlebotomy, and imaging contrast.

- Risk Level: Likely but not serious:
  - Risks from a skin puncture (perineum) include some discomfort associated with percutaneous analgesia and a risk of bruising, small scar formation, and a small chance of infection.
  - Voiding irritation frequency and urgency after the procedure secondary to urinary catheter which should be self resolving within a few days if removal.
  - Urinary retention after catheter removal.

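### Does Section 8 need a named interval method and a planned confidence interval for the toxicity rate, given that 80% interval widths justify the 15 patients?

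*Combined protocol and SAP*

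**What the plan says.** The sample size paragraph of Section 8 says "The sample size is targeted at 15 evaluable patients which is adequate to assess the toxicity rate". It gives two grounds. One is precision: "the width of the 80% expected confidence interval of 0.1 and 0.2 toxicity rate is 0.19 and 0.26, respectively". The other is that 15 patients can be recruited in six months. The paragraph does not say how the interval is calculated, whether it is two-sided, or in what sense the width is expected.

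The analysis text at the end of Section 8 says "Frequency of the outcome measures, response and toxicity will be reported", and adds descriptive statistics, such as frequencies and percentages, for categorical variables. It then turns to paired t tests, exploratory McNemar tests and mixed models for changes from baseline and over follow-up. The sample size sentence is the only mention of a confidence interval in the document.

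**The concern.** Safety is part of the primary objective (Section 1.1.1), and Section 8 makes toxicity part of its primary goal. When a sample size rests on the precision of an estimate, one expects the analysis to report that precision by the same method. Here the method is unnamed and the interval is unplanned.

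At 15 patients this is more than a formality. Methods that agree in large samples differ here, and they differ most when no event is seen. If the true rate were 0.1, no events in 15 patients would occur in about one trial in five. A bare zero would not tell the reader that rates up to 0.10 or 0.14 remain compatible with the data at the plan's own 80% level. A Wald interval, one candidate for the method behind the stated widths, would collapse to zero width. If the method is chosen after the data are seen, the reported upper limit could depend on that choice. At stake is how the main safety result is read.

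**Working it through.** **Inputs** (all from Section 8): n = 15; level 80%; assumed rates 0.1 and 0.2; stated widths 0.19 and 0.26. Assumption: the interval is two-sided, so z = 1.2816.

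**Step 1: reproduce the stated widths.**

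Wald at the assumed rate, 2z√(p(1−p)/n):
- p = 0.1: 2 × 1.2816 × √(0.09/15) = 2.5631 × 0.07746 = 0.1985
- p = 0.2: 2 × 1.2816 × √(0.16/15) = 2.5631 × 0.10328 = 0.2647

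These match the stated pair if cut to two decimals; rounded, they are 0.20 and 0.26.

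Arcsine at the assumed rate, sin²(a + d) − sin²(a − d), with a = arcsin√p and d = z/(2√n) = 0.1654:
- p = 0.1: a = 0.3218; 0.2192 − 0.0242 = 0.195
- p = 0.2: a = 0.4636; 0.3462 − 0.0863 = 0.260

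Unrounded, these are 0.1949 and 0.2599, which round to 0.19 and 0.26. The figures in Section 8 are therefore not an error, although the text does not show which method was used.

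**Step 2: average widths over the possible results.** For each method, the width at each count k is weighted by the Binomial(15, p) probability of k. Coverage is the total probability of the counts whose interval contains p.

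| Method | Width, p = 0.1 | Width, p = 0.2 | Coverage, p = 0.1 | Coverage, p = 0.2 | Upper limit at 0/15 |
|---|---|---|---|---|---|
| Wilson | 0.191 | 0.246 | 61.0% | 66.9% | 0.099 |
| Mid-P | 0.199 | 0.257 | 94.4% | 90.4% | 0.102 |
| Exact (Clopper-Pearson) | 0.243 | 0.303 | 94.4% | 90.4% | 0.142 |
| Wald | 0.167 | 0.247 | 73.9% | 77.2% | 0 |

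Mid-P differs from the stated widths by 0.009 and 0.003. Exact is larger by 0.053 and 0.043, that is 28% (0.243/0.19 = 1.28) and 17% (0.303/0.26 = 1.17). Only an exact interval would make the stated precision look clearly favourable.

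**Step 3: the zero-event case.** P(0/15) = 0.9^15 = 0.206 at rate 0.1, and 0.8^15 = 0.035 at rate 0.2. The exact 80% upper limit at zero is 1 − 0.1^(1/15) = 0.142. This needs only the count and n.

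**Step 4: does anything else depend on the interval?** The stopping rule is stated in event counts and uses no interval. Calculated exactly, with a check after each patient from the third onward, it stops with probability 0.0237 at rate 0.1 and 0.808 at rate 0.4. Section 8 gives 0.023 and 0.81. The sample size does not move either: the widths support 15 as stated, and recruitment is the second ground.

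**The case for a change.** The strongest case for a change is that the sponsor itself chose interval precision to justify 15 patients. Planning that interval would deliver what the justification implies, with no extra patient and no extra test, for two sentences of text. Naming the method in advance would also remove a choice made after the data are seen, and Step 2 shows that the choice is not neutral.

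The facts in that case stand: the method is unnamed, no interval is planned, and the method matters at n = 15. What does not follow is that the plan goes wrong without the change.

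- The count and the number treated determine every candidate interval, so a reader can compute one from the report. The descriptive statistics are introduced by example rather than as a closed list, so adding an interval would depart from nothing.
- Simply asking for some accepted small-sample method would not help. Wilson comes close to the stated widths, yet at both planning rates it covers less often than Wald. Its upper limit at 0/15 is 0.0987, which excludes a true rate of 0.1, the very rate that makes zero events a realistic worry. Mid-P and exact behave alike in coverage at these rates, so calling exact the conservative choice does not separate them.
- The zero-event worry depends on which events count. If toxicity means any grade, the 12-patient laser series in Section 6.3, with perineal discomfort in 25%, makes 0/15 improbable: 0.75^15 = 0.013. The definition of the event and of the denominator affects the reported rate more than the interval formula does.
- The stopping rule can end accrual before patient 15. At rate 0.2 this happens in 13.8% of trials if the rule is checked only after patients 5 and 10, and in 18.0% if it is checked after every patient. The 15-patient widths then do not apply, but reporting the actual number treated deals with that.

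**Conclusion.** No change to the plan is needed. Section 8 omits the name of the interval method and does not commit to reporting the interval. This is a detail that an analyst fills sensibly when writing up a 15-patient pilot. The stated widths of 0.19 and 0.26 are reproduced, neither the sample size nor the stopping rule depends on the missing detail, and the planned counts carry the information.

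The most that turns on it is the upper limit quoted beside the toxicity count: at zero events, 0.10 by mid-P or Wilson against 0.14 by the exact method. An analyst who adds an interval would do well to use mid-P or exact, to count every treated patient, and to state the actual number.

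The conclusion assumes a two-sided 80% interval and a report that gives the count with its denominator. The widths in Section 8 apply only if all 15 patients are treated.

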  - The safety and efficacy of gadolinium contrast has been well documented and a reaction is less likely while on protocol, due to all patients required an MRI with gadolinium to be evaluated as a possible candidate
  - Minimal risks are associated with the medical procedure of obtaining blood and include some discomfort and bruising.
- Risk Level: Unknown incidence but not serious
  - Erectile Dysfunction
  - Hematuria
- Risk Level: No known risk:
  - There are no known health hazards of ultrasound or MRI at power levels employed for diagnostic purposes
- Risk Level: Very unlikely, but serious:
  - Urinary fistula from ablation of the prostate with rectum.

The PI will continue to monitor the study along with reporting adverse events to the IRB. If there is mortality the study will be paused and a determination of cause will be pursued. If the cause was due to the laser therapy the pilot study will be concluded. Also, regarding other complications rates if the 30 day complication rate of serious events exceeds 2 patients a further analysis of the technique will be performed as well as pausing and possible concluding the study if changes cannot be made for improvement.

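### Section 8 and Sections 7.4.1/9.7 state different study-level actions in two narrow safety cases without saying which governs, and the stopping table counts events while its quoted probabilities belong to a count of patients

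*Combined protocol and SAP*

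**What the plan says.** **Death.** Section 8 (Stopping rule): "If one patient experiences a grade 5 event, thought to be possibly or probably due to the laser therapy, the study will be stopped". Section 7.4.1: "If there is mortality the study will be paused and a determination of cause will be pursued", followed by "If the cause was due to the laser therapy the pilot study will be concluded". Section 9.7 repeats the Section 7.4.1 rule.

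**Serious events.** Section 8: "For grade 3 or 4 event, the study will be stopped according to the following stopping rule". The table gives 3 events for 3-5 patients, 4 for 6-10 and 5 for 11-15, and its column header refers to the number of grade 3 or 4 serious adverse events. Section 7.4.1 sets a different trigger: "if the 30-day complication rate of serious events exceeds 2 patients a further analysis of the technique will be performed". The further consequence it names there is "as well as pausing and possible concluding the study if changes cannot be made for improvement". Section 9.7 has the same trigger: "if the 30 day complication rate of serious events exceeds 2 patients a further analysis of the technique will be performed".

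**General clause.** Section 7.4.1 also says "This study will be stopped, and the IRB will be notified if adverse events develop which endanger patient safety". It gives no threshold and does not refer to Section 8.

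**Operating characteristics.** From 10,000 simulations, Section 8 reports a stopping probability of 0.023 at a serious adverse event rate of 0.1 and 0.81 at a rate of 0.40. It does not say whether the simulation counted events or patients.

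**The concern.** Safety is part of the primary objective. Section 7.4.1 gives the interim assessments to the principal investigator and associate investigators, so the written rule is the main constraint on the decision. If two sections attach different actions to the same data and neither is given precedence, the action can be chosen after the events are known.

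The unit matters for a different reason. The two quoted probabilities are the only evidence offered that the rule is reasonable. If they describe a count of patients while the table tells the team to count events, the rule as written is not the rule that was evaluated.

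**Working it through.** **1. The actions side by side**

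| Situation | Section 8 | Sections 7.4.1 and 9.7 |
|---|---|---|
| Death established as due to the laser | Stop | Pause, then conclude |
| Death finally rated only possibly related | Stop | Pause; no instruction to conclude |
| Three patients among the first 3-5, events grade 3 or 4, serious and within 30 days | Stop | Further analysis, pause, possible conclusion |
| Three such patients, first reached at patients 6-15 | Below the boundary (4 or 5) if patients are counted | Further analysis, pause, possible conclusion |

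Row 1 agrees. Row 4 can work as a pause tier below a stop tier, although the text does not say so. Rows 2 and 3 differ. In row 3 both thresholds are three, so no tier separates them.

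**2. Reproducing the quoted probabilities**

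Inputs from Section 8: 15 patients; boundaries 3 (n = 3-5), 4 (n = 6-10) and 5 (n = 11-15); rates 0.1 and 0.40. I add 0.2 for illustration. Each patient counts at most once, with probability r.

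Because the boundary is constant within a row, checking after every patient gives the same result as checking at the row ends. With X_n the number of affected patients among the first n:

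P(stop) = 1 − P(X_5 ≤ 2, X_10 ≤ 3, X_15 ≤ 4)

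| Rate r | Stopped by patient 5 | By patient 10 | By patient 15 | Quoted |
|---|---|---|---|---|
| 0.1 | 0.0086 | 0.0176 | 0.0237 | 0.023 |
| 0.2 | 0.0579 | 0.1377 | 0.2055 | none |
| 0.4 | 0.3174 | 0.6356 | 0.8083 | 0.81 |

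The Monte Carlo standard error is √(q(1−q)/10,000): 0.0015 at q = 0.023 and 0.0039 at q = 0.81. The differences, 0.0007 and 0.0017, are under half a standard error. No other variant tried fits both figures:

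- boundary at patient 15 left out: 0.0211 and 0.762
- exceeding rather than reaching the boundary: 0.0034 and 0.614
- Poisson events with mean equal to the rate: 0.035 and 0.751

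**3. How often row 3 can arise**

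P(X_5 ≥ 3) = 10r³(1−r)² + 5r⁴(1−r) + r⁵

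- r = 0.1: 0.00810 + 0.00045 + 0.00001 = 0.0086
- r = 0.2: 0.0512 + 0.0064 + 0.0003 = 0.0579
- r = 0.4: 0.2304 + 0.0768 + 0.0102 = 0.3174

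These assume every event is grade 3 or 4, serious and within 30 days. If only half of affected patients meet both definitions (assumption; the documents give no split), use r/2: 0.0012, 0.0086 and 0.0579. Divided by all table stops (0.0237, 0.2055, 0.8083), the share is 36%, 28% and 39% if all qualify, and about 5%, 4% and 7% if half do.

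**4. Counting events literally**

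Hold the patient rate r fixed and let a fraction f of affected patients have two qualifying events. Per-patient counts are then 0, 1, 2 with probabilities 1−r, r(1−f), rf. The documents give no value for f.

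| f | r = 0.1 | r = 0.2 | r = 0.4 |
|---|---|---|---|
| 0 | 0.024 | 0.206 | 0.808 |
| 0.02 | 0.030 | 0.223 | 0.818 |
| 0.05 | 0.039 | 0.248 | 0.831 |
| 0.25 | 0.101 | 0.395 | 0.898 |
| 0.50 | 0.176 | 0.535 | 0.946 |

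For the same patients, an event count is never below a patient count, so it stops as early or earlier. Two patients with two events each among the first 10 give 2 × 2 = 4 events, which meets the table boundary. The Section 7.4.1 trigger of more than 2 patients is then not met.

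**The case against.** The best reply is that the rules can be obeyed together. Section 8 is mandatory and Sections 7.4.1/9.7 are permissive, so stopping at the Section 8 boundary satisfies both. For a possibly related death, Sections 7.4.1/9.7 are silent rather than contrary, and a pause can precede a stop. The general stop clause in Section 7.4.1 could be read as the principle that the Section 8 table puts into numbers. All this is fair, and it rules out the stronger inference that the sections cannot both be followed. What stands is that no section states this precedence: a team working from Section 7.4.1 alone could resume where Section 8 requires a stop.

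Three further inferences go beyond the documents:

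- **That more than a third of stops fall in the conflict.** The 36% and 39% shares need every event to be grade 3 or 4, serious and within 30 days.
- **That the quoted probabilities are wrong, or that event counting raises the low-rate figure several-fold.** Both quoted figures reproduce. The values 0.101 and 0.176 need repeats in 25% to 50% of affected patients, which nothing in the documents supports. Other wording also points to patients: the table is indexed by number of patients and the grade 5 rule speaks of one patient. Event counting also does not weaken protection, since it can only stop sooner.
- **That the table wrongly omits rectal or urethral damage and non-completion.** Section 8 labels these as relevant to stopping, but Section 3.7.1 uses similar wording on rectal or urethral damage, and lists grade 3 or 4 toxicity, for stopping an individual's laser procedure. Section 8 introduces its list as outcomes during treatment. Non-completion fits that reading less well, but the point is one to clarify, not a shown error.

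**Conclusion.** The concern holds in a limited form. The stated actions differ in rows 2 and 3 of the comparison, and precedence is not stated. The second of these cases is rare at a rate of 0.1 (0.001 to 0.009) and more frequent at 0.4 (0.058 to 0.317), the range depending on how many events meet both definitions. No probability can be put on the death case from the documents.

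The header and the quoted probabilities use different units. The probabilities are right for patients. Read as events, the figure at a patient rate of 0.1 moves from 0.024 to 0.030-0.039 if 2% to 5% of affected patients have two events (assumption), and further only if repeats are common.

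The calculations assume independent patients with a constant rate and each outcome known when the boundary is checked. Sample size, endpoints and planned analyses are unaffected.

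**What to change.** Reconcile Sections 7.4.1, 8 and 9.7 for both the death rule and the serious-event rule, and state how they relate and which governs when both are met. Thresholds and actions are for the sponsor to choose.

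Change the table header to patients with at least one qualifying grade 3 or 4 serious adverse event, which keeps 0.023 and 0.81 valid if the thresholds stay. Alternatively, keep events, state the assumed number per patient and re-simulate.

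In the same amendment, give the time window for the Section 8 count, since Sections 7.4.1/9.7 use 30 days and Section 8 sets none. As a clarification only, say whether the stopping-related items listed in Section 8 feed the study-level table or, as in Section 3.7.1, an individual's procedure.

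The cost is amendment wording, plus a short re-simulation if events remain the unit. No extra data are needed.

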## **PRÉCIS**

### ***Background:***

- Pilot study is designed to evaluate the safety and feasibility of thermal laser ablation of focal prostate tumors.
- Prostate cancer is relatively slow growing, with doubling times for local tumors estimated at 2 to 4 years.
- Some prostate cancers prove to be small, low grade, and noninvasive and they appear to pose little risk to the life or health of the host. Recent patient series suggest that 20% to 30% of men undergoing radical prostatectomy have pathologic features in the radical prostatectomy specimen consistent with an insignificant or "indolent" cancer which poses little threat to life or health.
- We propose that patients with low volume and low grade disease can be best served with focal ablation of the visible prostate cancer without the side effects of urinary incontinence and erectile dysfunction associated with radiation therapy or radical surgery.

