#### **1.1.2 Secondary Objective(s):**

- To evaluate tolerability of treatment
- To determine changes in imaging and biopsy characteristics after thermal ablation of localized prostate cancer
- To obtain preliminary data, as a follow-up to this study, regarding the effect of thermal ablation using Visualase on short and long term complication rates
- To compare Visualase estimates of thermal damage post contrast MRI images.
- Determine outcome of laser ablation for treatment of prostate cancer using serial PSA, PSA density, changes in imaging, IPSS, and SHIM.

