those patients who are diagnosed with indolent disease versus those with clinically significant disease. Active surveillance patients are usually diagnosed secondary to PSA screening at earlier stages with low levels of disease. Population epidemiology demonstrates that the majority of these patients will not develop clinically significant disease within their lifetimes. These individuals are then followed with routine PSA screening, DRE, and biopsy to monitor for progression of disease which may warrant delayed selective curative therapy such as surgery and/or irradiation in the event of progression. Patients with less aggressive disease remain on a monitoring protocol until their disease clinically progresses. Surveillance tools are essential for the identification of disease progression. We have used the criteria set forth by authors to select these patients for our trial. Klotz and colleagues selected patients with PSA < 15 and Gleason Score 3+4 or less, these patients were followed and intervention was determined if PSA doubling time was less than three years or an increase in Gleason score on biopsy, while being followed. Core length was not employed in our algorithm due to the fact that MR image guided biopsies have statistically significantly longer core length than traditional standard 12 core biopsies. Long term biopsy follow up protocol was a repeat at 1 year then biopsies at 3-4 year intervals.

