3.4.2.1.2 Day 1 post operatively

3.4.2.1.3 6 months

3.4.2.1.4 12 months, and

3.4.2.1.5 24 months, and 36 months after the treatment.

3.4.2.1.6 Then yearly thereafter for evaluation under the care of the local medical physician, but data will not be collected on this study (this utilizes the Cleveland clinic post operative imaging protocol used in kidney cancer).

3.4.2.2 Clinic Visits will occur at 3, 6, and 12, 18, 24 months post procedure, then yearly thereafter for a total of 3 years, and include:

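### PSA is tested only against the pre-ablation value, which in a single-arm ablation study cannot separate loss of PSA-producing tissue from cancer control

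*Combined protocol and SAP*

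**What the plan says.** The last secondary objective in section 1.1.2 reads: "Determine outcome of laser ablation for treatment of prostate cancer using serial PSA, PSA density, changes in imaging, IPSS, and SHIM". Section 8 gives the analysis: "Paired Student t test will be used to compare the difference between continuous variables (PSA, MRI imaging parameters) measured at baseline", continuing to each follow-up visit, after a transformation towards normality if needed. This is the only place in section 8 where PSA is named.

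Baseline PSA is drawn at screening or enrolment, before ablation (section 2.4 and Appendix D). The study is open, single-centre and non-randomised (section 3.1). PSA is repeated at the clinic visits of section 3.4.2.2: "Clinic Visits will occur at 3, 6, and 12, 18, 24 months post procedure, then yearly thereafter for a total of 3 years". That gives values at 3, 6, 12, 18, 24 and 36 months.

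Section 8 also proposes linear and non-linear mixed models with a random intercept and, if judged suitable, a random slope. They are to be explored only, they sit in the paragraph on questionnaire profiles, and neither PSA nor a post-ablation starting point is mentioned. No lowest value, PSA slope, doubling time or PSA failure definition is given for follow-up.

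A PSA doubling time appears once, in section 1.2, in the description of a cited surveillance series: "intervention was determined if PSA doubling time was less than three years or an increase in Gleason score on biopsy". The protocol says what it took from that literature: "We have used the criteria set forth by authors to select these patients for our trial".

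**The concern.** Ablation destroys gland tissue, benign and malignant, and that tissue makes PSA. PSA can therefore be expected to step down once, whether or not viable cancer remains. After that step, what bears on cancer control is whether PSA rises again. A test against the pre-ablation value adds the step and the later course together, and no control arm separates them.

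At stake is how the PSA result will be read. A significant fall at an early visit could be reported as treatment outcome when it mainly measures how much tissue was destroyed, even in a group whose remaining PSA is rising.

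**Working it through.** The plan states no expected fall, SD, significance level or power for PSA, so there is no planned figure to reproduce.

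**What the comparison measures.** Let f be the one-time fall as a fraction of baseline and DT the doubling time of all remaining PSA. At t years after ablation:

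PSA(t) / baseline = (1 − f) × 2^(t/DT)

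On the log scale the change from baseline is ln(1 − f) + t × ln 2 / DT. The first term is tissue loss; the second is the later course. A paired test at one visit estimates only their sum.

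**Time to regain baseline** = DT × log2(1/(1 − f)). The fall f is an assumption. DT = 3 years is borrowed from the cited surveillance series as a yardstick; DT = 2 years is an assumed faster case.

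| Assumed fall | DT = 3 years | DT = 2 years |
|---|---|---|
| 10% | 0.46 y | 0.30 y |
| 20% | 0.97 y | 0.64 y |
| 30% | 1.54 y | 1.03 y |
| 40% | 2.21 y | 1.47 y |
| 50% | 3.00 y | 2.00 y |

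Example: 3 × log2(1/0.6) = 3 × 0.737 = 2.21 years. If only a fraction c of the remaining PSA grows, the time is DT × log2(1 + f/((1 − f)c)), which is longer: with f = 20% and c = 0.5, 3 × log2(1.5) = 1.75 years.

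**What the group test would show.** Inputs: n = 15 (section 8); every man doubling every 3 years; SD of log-change 0.3 to 0.4 and two-sided 5%, both assumed. The probabilities come from the noncentral t with 14 degrees of freedom and noncentrality (mean log-change / SD) × √15. The range in each cell covers the two SDs.

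| Assumed fall | Significant fall, month 6 | Significant fall, month 12 | Significant rise, month 36 |
|---|---|---|---|
| 10% | 0.02 | below 0.01 | about 1 |
| 30% | 0.58 to 0.83 | 0.20 to 0.33 | 0.86 to 0.98 |
| 40% | 0.94 to above 0.99 | 0.71 to 0.92 | 0.38 to 0.59 |

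For the 40% case, the chance of a significant fall drops to 0.32 to 0.51 at month 18 and below 0.1 at month 24. With a 50% fall the mean only returns to baseline at month 36.

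**With a post-ablation reference.** If the fall is complete by month 3, the ratio to the month-3 value is 2^((t − 0.25)/3), which does not contain f. For DT = 3 years it is 1.06, 1.19, 1.33, 1.50 and 1.89 at months 6, 12, 18, 24 and 36.

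**The case against.** **Men with progressing cancer would be counted as treatment successes.** A reader might infer this, but the documents do not support it. Section 6.2 judges response by MRI enhancement, biopsy of the ablated sites and rectal examination; PSA is not a response criterion. Standard and targeted biopsies are scheduled at 12 and 24 months (section 3.4.2.3) and could find residual cancer whatever the PSA. The investigator's off-study criterion rests on a Gleason increase or disease beyond the prostate (section 3.7.2). The paired t test compares group means and classifies no one.

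**The trial ignores its own PSA trigger.** This does not hold either. The 3-year doubling time is the rule of a cited series, drawn on for patient selection; no PSA doubling-time rule applies after ablation here. The figure in the Précis, "with doubling times for local tumors estimated at 2 to 4 years", concerns tumours, not PSA, and is not used above.

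**Masking lasts one to three years.** At DT = 3 years that needs a fall of roughly 20% to 50%, which the documents do not supply. Their only ablation dimensions are canine means (section 1.2.5.2): 19.0 by 13.7 mm. As an ellipsoid this is π/6 × 19.0 × 13.7 × 13.7 ≈ 1,867 mm³, or 1.87 mL. One or two such zones in an assumed 30 to 60 mL gland are 3% to 12% of volume; if PSA falls in proportion, masking lasts 0.14 to 0.58 years. Four zones give 12% to 25% and 0.58 to 1.24 years. This gauge is rough, and tumour may make more PSA per mL, but it shows how far the answer depends on f.

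**Visit-by-visit testing would show the rebound.** For falls up to 40% the calculations agree, by months 24 to 36. That limits the problem mainly to early visits but does not make the early result interpretable.

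**PSA density.** The documents do not say density will be computed at months 3 and 18, so the absence of MRI at those visits contradicts nothing.

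**It is a 15-patient safety pilot.** True: no sample size, stopping rule or primary conclusion depends on PSA. But the plan chose to test PSA at every visit and named it as a treatment outcome, so the comparison should be one that can be interpreted.

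**Conclusion.** The concern holds in a limited form. The PSA comparison specified in section 8 does not answer the serial-PSA part of the secondary objective, because a change from the pre-ablation value in a single arm confounds tissue loss with cancer control. That is true for any size of fall.

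The practical size depends on assumptions outside the documents. With all remaining PSA doubling every 3 years, falls of 10% to 50% are regained in about 0.5 to 3.0 years, and sooner with faster doubling. Group comparisons at about months 3 to 12 could look favourable despite rising PSA if the fall is about 30% or more; at about 10% there is hardly any such effect. The significance probabilities are illustrations under an assumed SD and significance level. The consequence is confined to the PSA outcome and does not reach response, safety or feasibility.

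**What to change.** In section 8, analyse log-PSA from the first post-ablation value (month 3, or month 6 if the fall is not complete by then) through month 36, using a mixed model with random intercept and random slope. The random slope is needed: with a random intercept alone the model fits one common slope and cannot give individual doubling times. Report the mean slope with its confidence interval and each man's post-ablation slope or doubling time. The number of men under 3 years can be given descriptively only, not as a failure rule. Keep the change from the pre-ablation value, labelled as a description of the ablation step and not as evidence of cancer control.

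The cost is analysis-plan wording and modest extra analysis; all six post-ablation PSA values are already scheduled. Individual slopes from 15 men with at most six values each will be imprecise, and the PSA result may look less favourable than a change from baseline.
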